Exclusion criteria	
 a) Participants who have an established diagnosis of diabetes (Type 1, Type 2, Monogenic or secondary) b) Participants with a fasting glucose \geq 7mmol/l or a 2h value \geq 11.1 mmol/l c) Multiple pregnancies (twins, triplets etc.) as determined by scan d) Known intolerance to metformin e) Known contraindication to the use of metformin which include: 
 i. renal insufficiency (defined as serum creatinine of greater than 130 μmol/L or creatinine clearance $<$60 ml/min) ii. moderate to severe liver dysfunction (aspartate aminotransferase (AST) and alanine aminotransferase (ALT) greater than 3 times the upper limit of normal) iii. shock or sepsis, and iv. previous hypersensitivity to metformin f) Major congenital malformations or an abnormality deemed unsuitable for metformin by the site PI or attending consultant g) Known small for gestational age¹ h) Known current gestational hypertension or pre-eclampsia or ruptured membranes i) Participants who have a history of drug or alcohol use that, in the opinion of the investigator, would interfere with adherence to study requirements j) Participants with significant gastrointestinal problems such as severe vomiting, Crohn's disease or colitis which will inadvertently affect absorption of the study drug k) Participants with congestive heart failure or history of congestive heart failure l) Participants with serious mental illness which would affect adherence to study medication or compliance with study protocol in the opinion of the investigator m) Patients with rare hereditary problems of galactose intolerance,

	
the Lapp lactase deficiency or glucose-galactose malabsorption
 
¹Small for gestational age (SGA) refers to fetal growth less than the 10th percentile (RCOG, 2014), or if foetal growth is deemed unsatisfactory by the treating obstetrician.

Type of control	Placebo
Number of participants	550 participants will be randomised across 3 sites (Galway University Hospital, Portiuncula University Hospital and Mayo University Hospital)

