688 usual care) versus usual care in 550 participants with Gestational Diabetes Mellitus (GDM) across

689 upto 3 sites in the Republic of Ireland, followed until 12 weeks post-partum (+/- 4 weeks).

690

691 Eligible participants will be randomised to one of two groups; treatment group or placebo group.

692

693 **8.1.1. Treatment Group**

694

695 Participants randomised to the metformin group will receive metformin 500mg OD, with the dose

696 titrated upwards every 2 days over 10 days increasing to a maximum of 2500mg metformin daily (5

697 tablets) or maximum tolerated dose, in addition to usual care (exercise and MNT), and taken until

698 delivery.

699

700 **8.1.2. Placebo Group**

701

702 Participants randomised to the placebo group will receive 1 placebo tablet OD, with the dose titrated

703 upwards every 2 days over 10 days increasing to a maximum of five placebo tablets daily, in addition

704 to usual care (exercise and MNT), and taken until delivery.

705

706 Participants will be followed up at 4 weeks (+/- 7days) and at 12 weeks (+/- 4 weeks) post-partum for

707 additional maternal and neonatal outcomes.

708

709 **8.1.3. Usual Care**

710

711 Both the treatment and metformin group will receive usual care which consists of medical nutritional

712 therapy (MNT) and information on exercise provided by the Diabetes team or trained delegate. The

[figure not shown]
713 Diabetes team or trained delegate will instruct participants on the use of a glucometer and the

714 participants will perform 7-point glucose testing before and 1 hour after meals and before bed.

715 Participants will be supported by telephone contact from the Diabetes team or trained delegate

716 weekly throughout gestation and attend at 2-4 weekly intervals at an antenatal/diabetes clinic. Usual
 717 care is outlined in more detail in section 9.1.1.
 718

719 Figure 1: Schematic Diagram of Trial Design
 720

721
 722

723

724 **8.2. Selection of Study Population**

725

726 **8.2.1. Population**

727

728 The population for the trial is pregnant participants between the ages of 18-50 years, with a diagnosis
729 of GDM up to 28 weeks gestation (+ 6 days).

730

731 Participants diagnosed using a 75g oral glucose tolerance test (OGTT) and International Association
732 of Diabetes in Pregnancy Study Groups (IADPSG) criteria for diagnosis will be eligible to be enrolled

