1210 site will instruct the participant to go back to the previous dose and then try again to increase the dose
1211 after 4-7 days. If the participant cannot tolerate the study medication at the higher dose, but can
1212 tolerate the study medication at a lower dose, the participant may continue at that lower dose for the
1213 treatment period.

1214 **9.1.3. Placebo Group**

1215 Participants randomised to the placebo arm will receive placebo in addition to usual care. Placebo will
1216 be titrated according to the dosing schedule to achieve the pre-specified glucose targets (fasting
1217 ≤5mmol/l, 1hour post prandial ≤ 7mmol/l). Placebo tablets will commence at 1 tablet per day and will
1218 be increased to a maximum of 5 tablets per day over 10 days as with the treatment group.

1219 **9.1.4. Requirement for Insulin**

1220 Insulin will be commenced in each group as per normal practice if 2 or more home glucose readings
1221 are outside the pre-specified glucose targets (fasting ≤ 5mmol/l, 1hour post prandial ≤ 7mmol/l)
1222 (without reason) despite maximum oral therapy and MNT at any clinic visit. For this reason, insulin is
1223 considered a non-IMP in this trial (see safety reporting for NIMP section 10.3.3.). If insulin is initiated,
1224 tablets will also be continued at the maximum tolerated dose. Off study metformin is unlikely to be
1225 used as this is not routine clinical practice currently. The intervention will continue up to birth of the
1226 infant or end of pregnancy due to pregnancy loss.

1227

1228 **9.2. Formulation, packaging, and handling**

1229 The IMPs are Glucophage (Metformin) 500mg film-coated tablets and placebo to match tablets
1230 supplied to the trial by the marketing authorisation holder Merck Santé (France).

1231

1232 The tablets will be repacked for the trial into bottles containing 170 active or placebo tablets and each
1233 bottle will be labelled according to Annex 13 requirements.
1234 The Sponsor has contracted MODEPHARMA for arranging the clinical trials packaging, labelling, QP
1235 release and distribution of trial IMPs in compliance with Good Manufacturing Practice (GMP) and
1236 Good Distribution Practice (GDP). Please refer to the Summary of product Characteristics and
1237 Investigational Medicinal Product Dossier (IMPD) for further details about the IMP manufacture and
1238 labelling.

1239

1240 **9.3. Storage of study treatments(s)**

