6.1 General Study design and Plan

The EMERGE study is a phase III, parallel, randomised double-blind, placebo-controlled, trial of metformin (in addition to usual care) versus usual care in 550 women with Gestational Diabetes Mellitus (GDM) across 2 sites in Ireland, followed until 12 weeks post-partum (+/- 4 weeks).

It will comprise 3 steps; 1) screening, 2) treatment, and 3) follow up. Eligible women will be randomised to one of two groups; treatment group or placebo group.

Women randomised to the metformin group will receive metformin 500mg Once Daily (OD), with the dose titrated upwards every 2 days over 10 days increasing to a maximum of 2500mg metformin daily (5 tablets) or maximum tolerated dose, in addition to usual care (exercise and MNT), and taken until delivery.

Participants randomised to the placebo group will receive 1 placebo tablet OD, with the dose titrated upwards every 2 days over 10 days increasing to a maximum

[figure not shown]
EMERGE NUIG-2016-01, Statistical Analysis Plan Version 1, 21/03/2023

of five placebo tablets daily, in addition to usual care (exercise and MNT), and taken until delivery.

Participants will be followed up at 4 (+/- 7days) and 12 weeks (+/- 4 weeks) post-partum for additional maternal and neonatal outcomes.

The control and metformin groups will receive usual care, which consists of medical nutritional therapy (MNT) and information on exercise provided by the Diabetes team. The Diabetes team or trained delegate will instruct women on using a glucometer, and the women will perform 7-point glucose testing before and 1 hour after meals and before bed. Women will be supported by telephone contact from the Diabetes team or trained delegate weekly throughout gestation and attend at 2-4 weekly intervals at an antenatal/diabetes clinic. Usual care is outlined in more detail in section 9.1.1 of the protocol.

EMERGE NUIG-2016-01, Statistical Analysis Plan Version 1, 21/03/2023

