10.4 Multicentre Studies

This is a two-center clinical study, with standardization of participant enrolment, data entry and adverse event reporting. Investigational sites will follow the requirements of a common protocol, data collection procedures and forms.

Given the nature of the intervention, women from the two centers are considered exchangeable. Demographic and baseline data will be presented by each centre in the CSR to explore differences in patient characteristics between the centers.

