14.5 Clinical Laboratory Evaluations

Lab tests will be completed at the randomisation visit, 32 gestational weeks (+/- 1 week) AND at 38 gestational weeks (+/- 1 week), and 12 weeks post-partum (+/- 4 weeks).

The following laboratory assessments will be analysed locally:

At randomisation: HbA1c, fasting glucose, Insulin, c-peptide, total cholesterol, High-Density Lipoprotein (HDL) cholesterol, Low-Density Lipoprotein (LDL) cholesterol, triglycerides (Tg), urea, creatinine, alanine aminotransferase (ALT), and aspartate transaminase (AST).

At 32 weeks gestation: HbA1c, fasting glucose, total cholesterol, HDL cholesterol, LDL cholesterol, Tg, urea, creatinine, ALT, and AST.

EMERGE NUIG-2016-01, Statistical Analysis Plan Version 1, 21/03/2023

At 38 weeks gestation: HbA1c, fasting glucose, total cholesterol, HDL cholesterol, LDL cholesterol, Tg, urea, creatinine, ALT, and AST.

At 12 weeks post-partum: fasting glucose, 2h glucose, fasting insulin, fasting c-peptide, HbA1c, total cholesterol, HDL cholesterol, LDL cholesterol, Tg.

Descriptive summaries (mean, SD, median, minimum, and maximum) of changes from baseline will be presented for clinical laboratory values by treatment group and visit for the Safety Population.

The number of participants (counts and percentages) with clinically significant laboratory abnormalities at each visit will be highlighted for each lab test, for the Safety Population by treatment group.

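### The Protocol names three sites, but the SAP describes two exchangeable centres and puts site in no model: reconcile the site text and add a site term, for a modest gain in precision

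*Protocol*

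**What the plan says.** **Number of sites.** The Synopsis gives "550 participants will be randomised across 3 sites (Galway University Hospital, Portiuncula University Hospital and Mayo University Hospital"). Protocol 8.1 is looser: "upto 3 sites in the Republic of Ireland, followed until 12 weeks post-partum (+/- 4 weeks"). SAP section 3 lists Protocol Version 6 among the documents reviewed, but SAP 6.1 has "550 women with Gestational Diabetes Mellitus (GDM) across 2 sites in Ireland" and SAP 10.4 has "This is a two-center clinical study, with standardization of participant enrolment, data entry and adverse event reporting". The SAP does not name the two sites or explain the difference from the Synopsis.

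**Use of centre.** SAP 10.4 continues: "Given the nature of the intervention, women from the two centers are considered exchangeable". Its only planned use of centre is to present demographic and baseline data for each one.

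**Allocation.** The Synopsis, Protocol 8.5 and SAP 6.3 name BMI and previous GDM as the balancing factors. They describe permuted blocks of varying length without saying whether these ran within site.

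**Models.** The primary logistic model (SAP 13.1) adjusts for BMI, past GDM and other patient characteristics as appropriate. The secondary models (SAP 13.2) adjust for the stratification variables and relevant baseline characteristics. The interaction variables (SAP 10.6) are race, age, previous GDM and first pregnancy. Site is named in none of these.

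**Outcome.** On the first component, Protocol 9.1.4 says "Insulin will be commenced in each group as per normal practice if 2 or more home glucose readings" fall outside the stated targets. Protocol 9.1.1 adds that a growth scan contributes to the decision. On the second, the fasting glucose, SAP 14.5 says "The following laboratory assessments will be analysed locally".

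**The concern.** The stated reason for ignoring centre is that women from two unnamed centres are exchangeable. If three hospitals randomised women, that statement does not describe the trial. If two did, the Synopsis is out of date. The reader cannot tell which.

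The reason also addresses the intervention, whereas the question is whether the outcome could differ by site. Starting insulin combines a numeric trigger with clinical review. The glucose component is a hard cut at 5.1 mmol/l on locally analysed samples. Either could differ between hospitals at the same underlying glycaemia. Mode of delivery and neonatal unit care, both secondary outcomes, also depend on clinicians' decisions.

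At stake is some precision in the primary estimate. In addition, no planned output would show the primary event rate by site.

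**Working it through.** **1. The site text side by side**

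| Item | Protocol | SAP |
|---|---|---|
| Sites | three named (Synopsis); up to three (8.1) | two, unnamed (6.1, 10.4) |
| Deliveries per year | 7,000 (11.2) | 13,000 (section 7) |
| Expected GDM cases per year | up to 840 | 1,560 |

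Each case count follows from its own input at 12% prevalence: 7,000 × 0.12 = 840 and 13,000 × 0.12 = 1,560. So neither is an arithmetic slip. The two documents describe different catchments, by a factor of 13,000/7,000 = 1.86.

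**2. The plan's sample size**

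Inputs from Protocol 11.2 and SAP section 7: 40% v 28%, alpha 0.05 (taken as two-sided), 80% power, 5% drop-out, 8% non-adherence.

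n per arm = [1.96√(2 × 0.34 × 0.66) + 0.8416√(0.40 × 0.60 + 0.28 × 0.72)]² / 0.12² = 243.4, so 244 per arm and 488 in total. Then 488/0.95/0.92 = 559, close to the stated 550. Site does not enter this calculation, and adding a site term would not change N.

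**3. Chance site imbalance if blocks did not run within site**

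Take N = 535 (SAP 8.1), or 267.5 per arm. For a site with share p, the 95% limit on the between-arm difference in that share is 1.96√[p(1−p) × 2/267.5]. This is 6.8 points at p = 0.8 and 8.5 points at p = 0.5.

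The shift in the risk difference from imbalance has standard error √(V × 2/267.5), where V is the variance of the site rates. The documents give neither site shares nor site rates, so the following are assumptions:

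| Site rates | Shares | V | 95% limit of shift |
|---|---|---|---|
| 40/25/55% | 60/20/20 | 0.0090 | 1.6 points |
| 40/25/55% | 34/33/33 | 0.01485 | 2.1 points |
| 40/30/50% | 60/20/20 | 0.0040 | 1.1 points |
| 40/30/50% | 34/33/33 | 0.0066 | 1.4 points |

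For scale, the standard error of the risk difference is √(0.24/267.5 + 0.2016/267.5) = 0.0406, a 95% half-width of 8.0 points. Imbalance therefore accounts for about 4 to 7% of the variance in the wider case and 2 to 3% in the milder one. It is part of that half-width, not an addition to it.

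**4. Logistic regression with and without a site term**

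3,000 simulated trials per setting, N = 535, allocation not balanced by site, true odds ratio (0.28/0.72)/(0.40/0.60) = 0.583:

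| Shares | Assumed control rates | Type I error, without / with site | Power, without / with site | Mean odds ratio without site |
|---|---|---|---|---|
| 80/20 | 40/40% | 0.049 / 0.048 | 0.838 / 0.836 | 0.581 |
| 80/20 | 38/48% | 0.045 / 0.046 | 0.828 / 0.829 | 0.584 |
| 80/20 | 36/56% | 0.052 / 0.048 | 0.822 / 0.829 | 0.592 |
| 50/50 | 30/50% | 0.047 / 0.047 | 0.802 / 0.815 | 0.597 |
| 70/15/15 | 36/45/55% | 0.052 / 0.054 | 0.825 / 0.835 | 0.590 |
| 34/33/33 | 25/40/55% | 0.044 / 0.046 | 0.793 / 0.821 | 0.600 |

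Monte Carlo error on type I error is about √(0.05 × 0.95/3,000) = 0.004, so every value is compatible with 0.05. With arms balanced within site, type I error was 0.044 to 0.057 without a site term and 0.048 to 0.059 with one.

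**The case against.** The strongest reply is that this is a documentation slip plus a preference. Much of it stands.

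- **Bias.** A reader might infer that a site imbalance could pass as a treatment effect. Under randomisation, chance imbalance is ordinary sampling error that the test and interval already cover, and the type I error in the simulations agrees.
- **Insulin starts.** A reader might infer that they follow local practice. Protocol 9.1.4 says normal practice and sets one trial-wide trigger; the targets (9.1.1) and the glucometer (8.4.7) are common. Local practice patterns are mentioned only for the bio-banking sub-study. Variation through clinical judgement is an inference.
- **Allocation.** A reader might infer that it was not balanced by site. The documents show only that site is not a listed factor.
- **Origin of the exchangeability sentence.** A reader might infer that it was written for other hospitals. The delivery count points that way. But Protocol 8.1 permits two sites, and the SAP, dated March 2023, already counts repeat randomisations, so it may describe the sites that actually recruited. The documents do not settle this.
- **Closed plan.** The covariate wording in SAP 13.1 and 13.2 could be stretched to include site, and presenting baseline data for each centre works for any number of centres.
- **Size.** A 30-point spread in site rates is 2.5 times the design effect and has no support in the documents. The simulations also omit BMI and past GDM, which the plan adjusts for and which may explain part of any site difference.

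The contradiction in the site text remains, and so does the absence of a pre-specified site term. Permission to adjust as appropriate leaves that choice open.

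**Conclusion.** The point holds as a reconciliation of the two documents plus an inexpensive improvement to the analysis. The number of sites and the delivery counts conflict in current text, and the SAP's ground for leaving centre out rests on a description that may not match the trial.

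The statistical cost of omitting site is small. Type I error stays near 0.05. Power rises by about 0 to 3 points with a site term when control rates differ by up to 30 points between sites, and not at all when they do not differ. The odds ratio without site moves from 0.583 to at most 0.60, a slight attenuation towards 1. These sizes rest on assumed site shares and rates, on insulin rates of 40% and 28% standing in for the composite outcome, and on allocation not balanced by site.

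The documents do not support reading this as a biased or invalid primary test. The change is worth making because it is sound either way. If blocks ran within site, the SAP's own practice of adjusting for stratifying variables calls for a site term. If they did not, the term removes chance imbalance.

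**What to change.** - Reconcile the Synopsis, Protocol 8.1 and 11.2, and SAP 6.1, 7 and 10.4: name the sites that randomised women, give the number at each, and correct the delivery figure that does not apply. If only two sites recruited, say so and keep the site term below.
- State in SAP 6.3 whether the permuted blocks ran within site.
- Delete the exchangeability sentence from SAP 10.4.
- Add site as a fixed factor to the primary logistic model, the proportional hazards model for time to insulin, and the SAP 13.2 models. Merge a site with another only if it is too sparse to fit.
- Report the primary event rate by site and arm.

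Settle this before the randomisation codes are used for the primary analysis described in SAP 8.2.

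The cost is SAP wording, one or two degrees of freedom and a little more analysis. No new data are needed, since the by-centre tables in SAP 10.4 already require each woman's site.

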447 maternal and neonatal outcomes (O Sullivan 2011). In particular, maternal hypertensive disorders
448 were increased 2 fold (OR 1.5 CI 1-2), and delivery by Caesarean section increased by 30% (OR 1.3
449 CI 1-1.6). There was a significant increase in macrosomia (birth weight > 4 kg) at 23.9% compared to
450 17% in women without diabetes ($P < 0.05$) and also in the delivery of LGA babies ($> 90^{\text{th}}$ centile) at
451 22.6% compared to 16.2% in normal glucose tolerant (NGT) women ($P < 0.01$). The admission rate to
452 neonatal unit care (NNU) was 26% compared to 9.1% in NGT women ($P < 0.0001$) and the main
453 reason for admission was hypoglycaemia at a rate of 2.4% compared to 0.6% in NGT women
454 ($P < 0.0001$). Obesity in pregnancy was shown to be a growing problem contributing to GDM but also
455 causing significant independent morbidities for the mother and infant (Dennedy 2012). Caesarean
456 deliveries increased in overweight (OW) and obese (OB) women significantly with OR of 1.57 (CI
457 1.24-1.98) and 2.65 (OR 2.03-3.46) respectively. Hypertensive disorders in pregnancy were also
458 greater with an OR of 2.3 (CI 1.55-3.4) and 3.29 (CI 2.14-5.05) in OW and OB women respectively.
459 Mean birth weight was 3.46Kg in offspring of normal BMI women rising to 3.56kg and 3.62 kg in OW
460 and OB women respectively ($P < 0.01$). Macrosomia occurred in 15.5%, 21.4% and 27.8% of normal
461 OW and OB women respectively ($P < 0.01$). The cost of diagnosing and managing GDM in Ireland is

462 substantial (Gillespie 2013). GDM pregnancies incur an additional cost of circa 30% driven mainly by
463 NNU care admissions and delivery by Caesarean section. Obesity is also a significant contributor to
464 costs.

465

466 **6.1.4. Why is Gestational Diabetes Mellitus Clinically Important in the Long Term?**

467

468 Atlantic DIP found persistent glucose abnormalities in 19% of GDM women in the first 6 month's post-
469 partum compared with 2.7% in women with NGT in pregnancy (O Reilly 2011). Gestational insulin use
470 increased the chance of having persistent post-partum glucose abnormalities (OR 2.62; CI 1.17-5.87),
471 while breast-feeding compared to bottle feeding had a protective effect (8.2% vs. 18.4%; P<0.001) (O
472 Reilly 2011). Women were again rescreened up to 5 years post the index pregnancy (mean 2.6 years)
473 and on-going glucose abnormalities were present in 26% of women with prior GDM compared to 4%

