- 980 • Any longstanding medical condition for which the participant is currently taking treatment

981

982 A review of all concomitant medications will be documented by interview or review of medical records
983 at the screening visit. Changes in medical history and concomitant medications will be reviewed at
984 each subsequent visit.

985

986

987

988

989 **8.4.3. Physical Assessments**

990
991 Standardised measurement of BP will be used. Weight will be measured in kg, height in meters and
992 body mass index (BMI) as kg/m². BMI will be calculated categorised according to World Health
993 Organization (WHO) standards: underweight, <18.5 kg/m²; normal, 18.5–24.5 kg/m²; overweight
994 (OW), 25–29.9 kg/m²; obese (OB), >30 kg/m². Waist circumference will be taken using a tape
995 measure half way between the hip bone and the lowest rib, about 5 cm (2 in) above the belly button.
996

997 **8.4.4. OGTT**

998
999 A 75g OGTT will be carried out at screening and 12 weeks (+/- 4 weeks) post-partum.
1000 The OGTT at screening will determine the presence of GDM according to IADPSG/WHO 2013 criteria
1001 based on any one of the following values: Fasting >/= 5.1 and <7, 1 h >/=10, and 2h >/= 8.5 and
1002 <11.1 mmol/l. Results of the post -partum OGTT will categorize participants as one of the following: 1)
1003 Negative: fasting blood glucose (FBG) < 5.6 mmol/l, 2h blood glucose <7.8 mmol/l; 2) Impaired fasting
1004 glucose (IFG) FBG >5.6 <7mmol/l; 2h blood glucose <7.8mmol/l. 3) Impaired glucose tolerance FBG
1005 5.6-7mmol/l; 2h blood glucose 7.8-11.1mmol/l. 4) Diabetic FBG >7mmol/l or 2h blood glucose
1006 >11.1mmol/l. We will use a fasting venous sample as venous glucose is more accurate than capillary
1007 measurements.
1008

1009 **8.4.5. Laboratory Tests**

1010
1011 Lab tests should be completed at the randomisation visit, 32 gestational weeks (+/- 1 week) AND at
1012 38 gestational weeks (+/- 1 week), and 12 weeks post-partum (+/- 4 weeks). If the participant is
1013 administered steroids at 32 weeks gestation or 38 weeks gestation, defer lab tests for 48 hours.
1014

1015 The following laboratory assessments will be analysed locally:
1016

1017 Randomisation: HbA1c, fasting glucose, Insulin, c-peptide, total cholesterol, high density lipoprotein
1018 (HDL) cholesterol, low density lipoprotein (LDL) cholesterol, triglycerides (Tg), urea, creatinine,
1019 alanine aminotransferase (ALT), and aspartate transaminase (AST).
1020

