1021 32 weeks gestation: HbA1c, fasting glucose, total cholesterol, high density lipoprotein (HDL)
1022 cholesterol, low density lipoprotein (LDL) cholesterol, triglycerides (Tg), urea, creatinine, alanine
1023 aminotransferase (ALT), and aspartate transaminase (AST).
1024

1025 38 weeks gestation: HbA1c, fasting glucose, total cholesterol, high density lipoprotein (HDL)
1026 cholesterol, low density lipoprotein (LDL) cholesterol, triglycerides (Tg), urea, creatinine, alanine
1027 aminotransferase (ALT), and aspartate transaminase (AST).
1028

1029 12 weeks post-partum: fasting glucose, 2h glucose, fasting insulin, fasting c-peptide, HbA1c, total
1030 cholesterol, high density lipoprotein (HDL) cholesterol, low density lipoprotein (LDL) cholesterol,
1031 triglycerides (Tg).
1032

1033 **8.4.6. Bio-banking**

1035
1036 Participants at all trial sites will also be invited to partake in a GDM bio-banking sub-study which
1037 involves obtaining maternal blood samples at randomisation and gestational age 38 weeks (+/- 1

1038 week) and also a cord blood sample at delivery. This is executed under a separate Ethics Committee
1039 approved protocol and is executed as guided by local practice patterns and the availability of
1040 resources (including staff).

1041

1042 **8.4.7 Glucometer data**

1043

1044 Home capillary blood glucose measurements will occur as per routine practice in both groups using a
1045 Contour Next One Glucometer (Ascensia). Capillary glucose values will be downloaded from the
1046 glucometer at a subsequent in person study visit. The downloaded glucometer data will be stored and
1047 analysed as part of a future observational study, and will not be monitored as part of trial care. All
1048 clinically relevant glucometer readings will be reviewed at each on-site visit, as per usual care.

1049

1050 **8.4.8. Study Drug Accountability**

1051

1052 A pill count will be performed by the study nurse/site staff at prenatal visits every 4 weeks and at the
1053 12 week post-partum visit to facilitate study medication accountability and check compliance.

1054 Non-compliance is defined as less than 80% drug adherence of the participants maximum tolerated
1055 dose.

1056 **8.4.9. Neonatal Measurements**

1057

1058 The neonatal anthropometric measurements will be taken within 72 hours of delivery by trained
1059 personnel and will include:

- 1060 • Crown-heel length
- 1061 • Head circumference
- 1062 • Weight

1063

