5.2.2 Secondary endpoints

The secondary outcomes:

1. Time to insulin initiation and insulin dose required
2. Maternal morbidity at delivery (hypertensive disorders, antepartum and postpartum haemorrhage)
3. Mode of delivery
4. Gestational age at delivery
5. Postpartum glucose status, insulin resistance, and metabolic syndrome

EMERGE NUIG-2016-01, Statistical Analysis Plan Version 1, 21/03/2023

6. Postpartum BMI, gestational weight gain, and waist circumference
7. Infant birth weight
8. Infant size (large/small/appropriate for gestational age)
9. Neonatal height and head circumference at delivery
10. Neonatal morbidities (Need for neonatal care unit, respiratory distress, jaundice, congenital anomalies, Apgar score)
11. Neonatal hypoglycaemia (defined as plasma glucose <2.6mmol/L on one or more occasions starting 30-60 minutes after birth)
12. Cost effectiveness and budget impact of metformin treatment in addition to usual care
13. Treatment acceptability (Diabetes Treatment Satisfaction Questionnaire DTSQ and Rowan questionnaires)
14. Glycemic control, measured by participant glucocometer.

Quality of Life determined by EQ5D-5L questionnaire

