13.2 Secondary Efficacy Analyses

Secondary efficacy outcomes include:

- Maternal morbidity at delivery (hypertensive disorders, antepartum and postpartum haemorrhage)
- Mode and time of delivery
- Maternal post-partum BMI, waist circumference, maternal gestational weight gain (GWG) blood glucose status, insulin resistance status and metabolic syndrome postpartum
- Proportion of maternal morbidities
- Infant birth weight
- Infant size (large/small/appropriate for gestational age)
- Neonatal height and head circumference at delivery
- Neonatal morbidities (Need for neonatal care unit, respiratory distress, jaundice, congenital anomalies, Apgar score)
- Neonatal hypoglycaemia (defined as plasma glucose <2.6mmol/L on one or more occasions starting 30-60 minutes after birth)

EMERGE NUIG-2016-01, Statistical Analysis Plan Version 1, 21/03/2023

- Proportion of infants with morbidities
- Treatment acceptability (Diabetes Treatment Satisfaction Questionnaire DTSQ and Rowan questionnaires)
- Quality of Life determined by EQ5D-5L questionnaire

Exploratory analyses based on generalised linear models will be used to estimate the treatment effect for each of the secondary outcomes while adjusting for the stratification variables and relevant baseline characteristics.

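### The SAP specifies no between-arm estimate for post-partum fasting or 2-hour glucose as continuous outcomes; adding one beside the glucose-status category would be a cheap gain in precision

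*Protocol*

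**What the plan says.** - **Objective and endpoint.** The effect of metformin on post-partum glucose status is part of secondary objective 3 (Protocol 7.2, SAP 5.1.2). SAP 5.2.2 lists the endpoint as "Postpartum glucose status, insulin resistance, and metabolic syndrome", and SAP 13.2 repeats it as "blood glucose status, insulin resistance status and metabolic syndrome postpartum".
- **Definition.** The only definition of a post-partum glucose status is in Protocol 8.4.4: the "OGTT will categorize participants as one of the following", namely negative, impaired fasting glucose, impaired glucose tolerance or diabetic. SAP 5.3 derives birth-weight centiles and nothing for glucose.
- **Data collected.** SAP 14.5 lists, "At 12 weeks post-partum: fasting glucose, 2h glucose, fasting insulin, fasting c-peptide, HbA1c" and lipids. Protocol 8.4.5 has the same list.
- **Between-arm method.** SAP 13.2: "Exploratory analyses based on generalised linear models will be used to estimate the treatment effect for each of the secondary outcomes", adjusted for the stratification variables and relevant baseline characteristics. No family, link or scale is given for any one outcome.
- **Numerical values.** SAP 14.5: "Descriptive summaries (mean, SD, median, minimum, and maximum) of changes from baseline will be presented for clinical laboratory values by treatment group and visit", in the Safety Population. No estimate of treatment effect, interval or test is attached.

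**The concern.** A four-way classification of two continuous measurements ignores how far each woman lies from the cut-points. Protocol 6.1.4 reports "persistent glucose abnormalities in 19% of GDM women in the first 6" months post-partum in an observational cohort. If the trial is similar, about four women in five fall in one category, and differences within that group contribute nothing to a categorical comparison.

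The visit may also be thinly attended: the sample-size section plans for up to 50% loss for post-partum weight change. A categorical comparison on a sample of that size could miss a moderate effect and be reported as no post-partum glycaemic effect. Because the SAP is silent on scale, the choice between category and continuous value could also be made after allocation is known.

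**Working it through.** **1. The plan's own post-partum figure.** No power is stated for the OGTT outcome. The one power statement for this visit concerns weight change: 138 per arm, 1.36 kg, SD 4 kg, alpha 0.05, 80% power. Two-sided testing is assumed, since the documents do not say.
- n per arm = 2 × (1.960 + 0.842)² × (4/1.36)² = 136 (137 by t-test).
- Power at 138 = Φ(0.34 × √69 − 1.96) = 80.6%.

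The stated figure reproduces. The standardised shift is 1.36/4 = 0.34 SD. The number per arm is 550 × 0.5 / 2 = 137.5, rounded to 138.

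**2. Information kept by a split.** For a normal variable under a location shift, a two-category split with abnormal proportion p and cut-point z keeps φ(z)² / [p(1 − p)] of the information.
- p = 19% (Protocol 6.1.4, first 6 months): z = 0.878, φ = 0.2714. Then 0.2714² / (0.19 × 0.81) = 0.478.
- p = 26% (Protocol 6.1.4, up to 5 years; used as an upper value): z = 0.643, φ = 0.3244. Then 0.3244² / (0.26 × 0.74) = 0.547.
- p = 10% keeps 34%; p = 50% keeps 64%.

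Four ordered categories keep the sum over categories of (difference in φ at the two boundaries)² / category proportion. With an assumed split of 81/10/7/2%: 0.2714²/0.81 + (0.1624 − 0.2714)²/0.10 + (0.0484 − 0.1624)²/0.07 + 0.0484²/0.02 = 0.51. At 26% abnormal, with an assumed 74/14/9/3% split, it is 0.60.

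**3. Power illustration.** The plan gives no expected effect on post-partum glucose, so the shift d is an assumption, varied from 0.10 to 0.34 SD.
- Continuous: Φ(d√(n/2) − 1.96), for one measure tested alone.
- Abnormal v normal on one measure: control proportion p, treated proportion P(Z > z + d), two-proportion normal approximation with pooled null variance.
- Abnormal on either fasting or 2-hour glucose: bivariate normal, correlation 0.3 to 0.7, equal cut-points set so that P(either) = p, both means shifted by d.

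Worked case, n = 138, d = 0.34, p = 19%: treated proportion = P(Z > 1.218) = 11.2%; difference 0.0784; null SE 0.0431; alternative SE 0.0428; power = Φ((0.0784 − 1.96 × 0.0431)/0.0428) = 44%.

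| n per arm | Abnormal in controls | Shift (SD) | One measure, split | Either measure, split | Continuous |
|---|---|---|---|---|---|
| 138 | 19% | 0.34 | 44.4% | 47.4-51.4% | 80.6% |
| 138 | 26% | 0.34 | 50.8% | 54.3-59.1% | 80.6% |
| 138 | 19% | 0.25 | 27.6% | 29.6-32.4% | 54.6% |
| 138 | 19% | 0.15 | 13.1% | 13.9-15.1% | 23.8% |
| 138 | 19% | 0.10 | 8.1% | 8.5-9.1% | 12.9% |
| 187 (30% loss from 535) | 19% | 0.34 | 56.3% | 59.8-64.3% | 90.8% |
| 254 (5% loss from 535) | 19% | 0.34 | 69.5% | 73.1-77.4% | 96.9% |

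The continuous comparison has more power in every row. The gain ranges from about 4 points at 0.10 SD to about 36 points at 0.34 SD.

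**4. Baseline.** Protocol 8.4.5 measures fasting glucose at randomisation but not 2-hour glucose. A change from baseline in 2-hour glucose can therefore come only from the screening OGTT, and SAP 14.5 does not say so. SAP 13.2 could admit screening values as relevant baseline characteristics but does not name them.

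**The case against.** The strongest reply is that the plan has not chosen to throw anything away. The sentence in Protocol 8.4.4 belongs to a description of procedures: it says how an OGTT result is classified, not how arms are compared. A reader might infer that the arms are compared only as categories. The documents do not say that: SAP 13.2 leaves the scale open, and SAP 14.5 shows the numerical values by arm. This stands. What is missing is a specified estimate, not permission to make one.

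The category also answers its own question. Protocol 6.1.4 is about persistent glucose abnormality, and the share of women with impaired glucose or diabetes is a legitimate outcome. A mean difference in mmol/l, mostly among women in the normal range, is a different quantity. This stands too, and is why the category comparison should be kept rather than reduced to counts.

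The size is conditional. The 0.34 SD shift comes from body weight, and nothing in the documents supports it for glucose 12 weeks after study drug stops. The 50% loss is a worst case stated for weight; the target is follow-up above 95%, and with the revised total of 535 the worst case is about 134 per arm. Protocol 6.1.4 does not give the cut-points behind its 19%. These points limit the magnitude but do not reverse the direction.

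Finally, the outcome is exploratory and carries no power claim. That lowers the priority; it does not remove the gap.

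**Conclusion.** The point holds as a cheap improvement, not as an error. The only defined efficacy variable for post-partum glucose is the four-category status, and no between-arm estimate of continuous fasting or 2-hour glucose is specified.

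The information kept by an abnormal/normal split, about 48% at 19% abnormal and 55% at 26%, assumes normality, a pure location shift, one glucose variable and a formal analysis limited to that split. It should not be read as a statement that the plan discards half the information: the SAP does not impose that limit, four ordered categories keep somewhat more, and the figure moves with the abnormal rate. The contrast of 44-51% with 81% power is an illustration at an assumed 0.34 SD and 138 per arm. At 0.15 SD both analyses are weak (about 14% against 24%), so the continuous analysis would not rescue a small effect.

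**What to change.** In SAP 13.2:
- Keep the between-arm comparison of glucose status, and state the scale and model used for it.
- Add fasting glucose and 2-hour glucose at 12 weeks post-partum as two continuous outcomes in the ITT set. Use the generalised linear model already planned (Gaussian, identity link), adjusted for the matching screening OGTT value, BMI group and past GDM. Report mean differences with 95% CIs.
- Label both as exploratory and settle the wording before post-partum data are analysed by arm.

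The cost is SAP wording and two model fits on data already collected; no visit, sample or procedure changes. The downside is two more exploratory estimates with no multiplicity adjustment (SAP 10.5 plans none).

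A separate matter affects the category itself. The four groups in Protocol 8.4.4 do not cover every result: for example, fasting glucose below 5.6 mmol/l with a 2-hour value of 7.8-11.1 mmol/l fits none. The definitions need reconciling before the category is analysed. The continuous outcomes do not depend on that.
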